15.6.3. SLEDAI-2K Total and Organ System Domain

| SLEDAI-2K Total and Organ System Domain Scores | | | | | | | | | | | |
|---|--|--------|------------|--------------|------------|--------|------------|------------------|--|--|--|
| 
SLEDAI-2K assessments consist of 24 individual items in which signs and symptoms, laboratory tests, and physician’s assessment for each of 9 organ systems are given a weighted score and summed if present (marked ‘Yes’) at the time of the visit or in the preceding 10 days. The maximum theoretical score is 105 (all 24 descriptors present simultaneously) with 0 indicating inactive disease (marked ‘No’).
 
Organ system domain scores are the sum of the weights of items within the organ domain as defined in Table 9.
 
In this study, proteinuria is evaluated using spot-urine protein [represented as protein-creatinine ratio or PC Ratio in the laboratory dataset]. in lieu of the 24-hour urine collection, as evaluated by the investigator.
 | | | | | | | | | | | |
| 
Table 9 SLEDAI-2K
 
  
 Organ System	Descriptor	Weight	Definition	
   
 CNS^a	 
CCI - This section contained Clinical Outcome Assessment data collection questionnaires or indices, which are protected by third party copyright laws and therefore have been excluded.
 	
  
 | | | | Organ System | Descriptor | Weight | Definition | CNS ^a | 
CCI - This section contained Clinical Outcome Assessment data collection questionnaires or indices, which are protected by third party copyright laws and therefore have been excluded.
 | | |
| Organ System | Descriptor | Weight | Definition | | | | | | | | |
| CNS ^a | 
CCI - This section contained Clinical Outcome Assessment data collection questionnaires or indices, which are protected by third party copyright laws and therefore have been excluded.
 | | | | | | | | | | |

| | |
|------------------------------|---|
| | CCI - This section contained Clinical Outcome Assessment data collection questionnaires or indices, which are protected by third party copyright laws and therefore have been excluded. |
| Vascular ^a | |
| Musculoskeletal | |
| Renal | |
| Mucocutaneous | |
| Cardiovascular & Respiratory | |
| Immunologic | |
| Constitutional ^a | |
| Hematologic ^a | |
| | |

The clinical SLEDAI-2K score (Excluding Serological Activity assessments) is the sum of **22 of the 24** individual items from the SLEDAI-2K, excluding the following 2 items:

| | |
|-------------|---|
| Immunologic | CCI - This section contained Clinical Outcome Assessment data collection questionnaires or indices, which are protected by third party copyright laws and therefore have been excluded. |
| | |

The scoring of the 22 questions is weighted in the same manner as the SLEDAI-2K, however the maximum theoretical score is now 101.

Note that the wording in the Protocol was “Serological activity score, i.e., anti-dsDNA positivity and/or hypocomplementemia, is excluded from the Clinical SLEDAI-2K endpoint”. The endpoint has been clarified here by using the names of the two SLEDAI-2K item scores, however, this does not represent a change to the planned endpoint, just a clarification.

Partial but informative SLEDAI-2K score

If after imputation for missing questions the SLEDAI-2K total score is still not derivable due to missing individual questions, then the minimum possible score will be considered (sum of the answered questions).

Similarly a maximum possible score (observed questions + maximum response for missing questions) will be considered.

15.6.4. Disease Control

| |
|---|
| Endpoint Definition |
| The disease control endpoint is defined as: 
 • SLEDAI-2K score ≤ 2 (IBA*), |

| |
|---|
| 
 • Not a Treatment failure • Not a Study withdrawal 
The same derivation will be applied to the secondary endpoint “Disease control (PI)” using the principal investigators assessment of the SLEDAI-2K.
 |
| 
Imputation of Missing values – IBA assessment
 |
| 
Missing IBA assessments based on laboratory assessments i.e.: Urinary Casts, Hematuria, Proteinuria, Pyuria, Low Complement, Increased DNA Binding, Thrombocytopenia, and Leukopenia will be imputed from the PI assessment if the laboratory sample (for the PI assessment) was drawn no more than 35 days prior. An imputed assessment can not be used to impute another assessment. There will be no imputation of missing IBA assessments based on physical examination
 |
| 
Imputation of Missing values – PI assessment
 |
| 
If an individual question of the SLEDAI-2K assessment or the full assessment is missed the previous assessment may be used as a substitute if it was no more than 35 days prior. An imputed assessment cannot be used to impute another assessment.
 |
| 
Partial but informative SLEDAI-2K score
 |
| 
If after imputation for missing questions the SLEDAI-2K total score is still not derivable due to missing individual questions, then the minimum possible score will be considered. If the minimum possible score is >2 then the subject will be considered as a non-responder. Similarly a maximum possible score will be considered to determine if the maximum possible score is ≤2.
 |
| 
Time to Disease Control Sustained to Week 104
 |
| 
A subject has a sustained disease control at a visit if all of the following criteria are met:
 
 1 In disease control at the visit 2 In disease control at the first visit that is at least 24 study weeks prior, or if disease control cannot be assessed at that visit, then in disease control at the visit prior. 3 In disease control for all assessed visits between (1) and (2). Note assessments can be missing. 
Note: 24 weeks refers to the difference in visit ‘labels’ not calendar weeks between visits. The first visit of sustained disease control is defined as the 1st visit that the subject is a disease control responder and all subsequent visits up to and including Week 104 the subjects is also a disease control responder. Missing assessments are not considered.
 
Time to disease control sustained to Week 104 = 1st visit of sustained disease control - treatment start date (Day 1) +1
 |
| 
Duration of Disease Control
 |
| 
The duration of disease control is defined as the longest period between 2 visits that the subject is a disease control responder at all visits. Missing assessments are not considered. Duration of disease control = longest period where 1st visit of disease control – last visit of disease control + 1
 |

| Example Subject | SLEDAI-2K score at Week 52 | Study Withdrawal (including Lost to Follow-up, or Death) prior to Week 52 | Treatment Failure prior to Week 52 | IP Discontinuation prior to Week 52 | Main Estimand (Hybrid) | Supportive Estimand (Composite) | (Hybrid On Treatment) | Treatment Policy |
|-----------------|---|---|------------------------------------|-------------------------------------|------------------------|---------------------------------|-----------------------|------------------|
| 1 | >2 | N | N | N | NR | NR | NR | NR |
| 2 | >2 | N | N | Y | NR | NR | Excluded | NR |
| 3 | >2 | N | Y | N | NR | NR | NR | NR |
| 4 | >2 | N | Y and prior to IP discontinuation | Y | NR | NR | NR | NR |
| 5 | >2 | N | Y but post IP discontinuation | Y | NR | NR | Excluded | NR |
| 6 | <=2 | N | N | N | R | R | R | R |
| 7 | <=2 | N | N | Y | R | NR | Excluded | R |
| 8 | <=2 | N | Y | N | NR | NR | NR | R |
| 9 | <=2 | N | Y and prior to IP discontinuation | Y | NR | NR | NR | R |
| 10 | <=2 | N | Y but post IP discontinuation | Y | NR | NR | Excluded | R |
| 11 | Incomplete* or entirely missing | N | N | N | NR | NR | NR | NR |
| 12 | Incomplete* or entirely missing but not due to study withdrawal | N | N | Y | NR | NR | Excluded | NR |
| 13 | Incomplete* or entirely missing but not due to study withdrawal | N | Y | N | NR | NR | NR | NR |
| 14 | Incomplete* or entirely missing but not meaningful | N | Y and prior to IP discontinuation | Y | NR | NR | NR | NR |
| 15 | Incomplete* or entirely missing but not due to study withdrawal | N | Y but post IP discontinuation | Y | NR | NR | Excluded | NR |
| 16 | Missing - does not exist due to study withdrawal | Y and at the same time as IP discontinuation | N | Y | NR | NR | NR | NR |

| Example Subject | SLEDAI-2K score at Week 52 | Study Withdrawal (including Lost to Follow-up, or Death) prior to Week 52 | Treatment Failure prior to Week 52 | IP Discontinuation prior to Week 52 | Main Estimand (Hybrid) | Supportive Estimand (Composite) | (Hybrid On Treatment) | Treatment Policy |
|-----------------|--|---|------------------------------------|-------------------------------------|------------------------|---------------------------------|-----------------------|------------------|
| 17 | Missing - does not exist due to study withdrawal | Y but post IP discontinuation | N | Y | NR | NR | Excluded | NR |
| 18 | Missing - does not exist due to study withdrawal | Y and at the same time as IP discontinuation | Y and prior to IP discontinuation | Y | NR | NR | NR | NR |
| 19 | Missing - does not exist due to study withdrawal | Y but post IP discontinuation | Y and prior to IP discontinuation | Y | NR | NR | NR | NR |
| 20 | Missing - does not exist due to study withdrawal | Y but post IP discontinuation | Y but post IP discontinuation | Y | NR | NR | Excluded | NR |

R = Responder; NR = Non-Responder

*Incomplete: does not include partial scores where it is possible to determine that the total score must be >2, or that the maximum possible score (assuming worst case for missing data) is <=2

15.6.5. Clinical Remission

| |
|--|
| 
Endpoint Definition
 
Clinical remission for Arms A & B (secondary endpoint) is defined as:
 
 • Clinical SLEDAI-2K score[#] = 0 (IBA*), • Not a Treatment Failure • Did not withdraw from the study • 7-day average corticosteroids at a prednisone equivalent dose of 0mg/day for the assessment (7 day average is the average of current and 6 previous days) 
[#]See Section 15.6.3
 
*at baseline the principal investigators assessment will be used
 
The same derivation will be applied to the secondary endpoint “clinical remission (PI)” using the principal investigators assessment of the SLEDAI-2K.
 |
| 
Imputation of Missing values – IBA assessment
 
Missing IBA assessments based on laboratory assessments i.e.: Urinary Casts, Hematuria, Proteinuria, Pyuria, Thrombocytopenia, and Leukopenia will be imputed from the PI assessment if the laboratory sample (for the PI assessment) was drawn no more than 35 days prior. An imputed assessment can not be used to impute another assessment.
 
There will be no imputation of missing IBA assessments based on physical examination
 |
| 
Imputation of Missing values – PI assessment
 
If an individual question of the SLEDAI-2K assessment or the full assessment is missed the previous assessment may be used as a substitute if it was no more than 35 days prior. An imputed assessment cannot be used to impute another assessment.
 |
| 
Partial but informative Clinical SLEDAI-2K score
 
If after imputation for missing questions the Clinical SLEDAI-2K score is still not derivable due to missing individual questions, then the minimum possible score will be considered (sum of the answered questions). If the minimum possible score is >0 then the subject will be considered as an observed non-responder (rather than non-responder due to missing data).
 |
| 
Clinical Remission Sustained For At Least 24 Weeks
 
Sustained response will be reported for all weeks post Week 52 (Year 2), and at any timepoint (i.e. any subjects who had a sustained response at any time during Year 2). Statistical analysis will only be conducted at Week 104 and at ‘any timepoint’.
 
A subject has a sustained remission at a visit if all of the following criteria are met:
 
 1 In clinical remission at the visit 2 In clinical remission at the first visit at least 24 study weeks prior, or if clinical remission cannot be assessed at that visit, then in clinical remission at the visit prior. 3 In clinical remission for all assessed visits between (1) and (2). – Note assessments can be missing. 
Note: 24 weeks refers to the difference in visit ‘labels’ not calendar weeks between visits.
 |

[figure not shown]
| |
|--|
| Time to Clinical Remission Sustained to Week 104 |
| The first visit of sustained clinical remission is defined as the 1 st visit that the subject is a clinical remission responder and all subsequent visits up to and including Week 104 the subjects is also a clinical remission responder. Missing assessments are not considered (the rules for sustained response for at least 24 weeks as defined above are also applied here). |
| Time to clinical remission sustained to Week 104 = 1 st visit of sustained clinical remission - treatment start date (Day 1) +1 |
| Duration of Clinical Remission |
| The duration of clinical remission is defined as the longest period between 2 visits that the subject is a clinical remission responder at all visits. Missing assessments are not considered Duration of clinical remission = longest period where 1 st visit of clinical remission – last visit of clinical remission + 1 |

15.6.6. Complete Remission

| |
|--|
| Endpoint Definition |
| Complete remission for Arms A & B (secondary endpoint) is defined as: 
 • SLEDAI-2K score = 0 (IBA*), • Not a Treatment Failure (specific to Arms A&B) • Did not withdraw from the study • 7-day average corticosteroids at a prednisone equivalent dose of 0mg/day for the assessment (7 day average is the average of current and 6 previous days) Complete remission for Arm C (the exploratory endpoint) is defined as: 
 • SLEDAI-2K score = 0 (IBA*), • Not a Treatment Failure (specific to Arm C) • Did not withdraw from the study • 7-day average corticosteroids at a prednisone equivalent dose of 0mg/day for the assessment (7 day average is the average of current and 6 previous days) *at baseline the principal investigators assessment will be used |
| Note some tables will contain the endpoint using these 2 different definitions in the same table. |
| Imputation of Missing values – IBA assessment |
| Missing IBA assessments based on laboratory assessments i.e.: Urinary Casts, Hematuria, Proteinuria, Pyuria, Low Complement, Increased DNA Binding, Thrombocytopenia, and Leukopenia will be imputed from the PI assessment if the laboratory sample (for the PI assessment) was drawn no more than 35 days prior. An imputed assessment can not be used to impute another assessment. There will be no imputation of missing IBA assessments based on physical examination |

| |
|--|
| Imputation of Missing values – PI assessment |
| If an individual question of the SLEDAI-2K assessment or the full assessment is missed the previous assessment may be used as a substitute if it was no more that 35 days prior. An imputed assessment cannot be used to impute another assessment. |
| Partial but informative SLEDAI-2K score |
| If after imputation for missing questions the SLEDAI-2K total score is still not derivable due to missing individual questions, then the minimum possible score will be considered (sum of the answered questions). If the minimum possible score is >0 then the subject will be considered as an observed non-responder (rather than non-responder due to missing data). |
| Complete Remission Sustained For At Least 24 Weeks |
| Sustained response will be reported for all weeks post Week 52 (Year 2), and at any timepoint (i.e. any subjects who had a sustained response at any time during Year 2). Statistical analysis will only be conducted at Week 104 and at ‘any timepoint’. A subject has a sustained remission at a visit if all of the following criteria are met: 
 1 In complete remission at the visit 2 In complete remission at the first visit at least 24 study weeks prior, or if complete remission cannot be assessed at that visit , then in clinical remission the visit prior. 3 In complete remission for all assessed visits between (1) and (2). – Note assessment can be missing. Note: 24 weeks refers to the difference in visit ‘labels’ not calendar weeks between visits. |

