| 
Secondary Objectives: Efficacy (Other)
 
 Secondary: Efficacy (Other) | 
Secondary Endpoints: Efficacy (Other)
 
 Proportion of participants with a state of disease control, defined as a SLEDAI-2K score (IBA) ≤2, achieved without immunosuppressants and with corticosteroids at a prednisone equivalent dose of ≤5 mg/day, by visit Proportion of participants with a state of clinical remission, defined as a Clinical SLEDAI-2K score (IBA) =0 (Section 15.6.3), achieved without immunosuppressants and with corticosteroids at a prednisone equivalent dose of 0 mg/day, by visit. Proportion of participants with a state of complete remission, defined as SLEDAI-2K score (PI) =0, achieved without immunosuppressants and with corticosteroids at a prednisone equivalent dose of 0 mg/day, sustained for at least 24 weeks. Proportion of participants with a state of clinical remission, defined as Clinical SLEDAI-2K score (PI) =0 (Section 15.6.3), achieved without immunosuppressants and with corticosteroids at a prednisone equivalent dose of 0 mg/day, sustained for at least 24 weeks. Proportion of participants with a state of complete remission, defined as a SLEDAI-2K score (PI) =0, achieved without immunosuppressants and with corticosteroids at a prednisone equivalent dose of 0 mg/day, by visit Time to first severe flare (as measured by the modified SLE Flare Index) Time to first flare (as measured by the modified SLE Flare Index) Time to disease control sustained to Week 104, defined as SLEDAI-2K score (PI) ≤2, achieved without immunosuppressants and with corticosteroids at a prednisone equivalent dose of ≤5 mg/day. |

| Objectives | Endpoints |
|------------|--|

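### The sustained complete remission rule falls back to clinical remission when the 24-week anchor visit is missing, so serological activity at the substitute visit is ignored

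*SAP*

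**What the plan says.** Section 2.2 of the SAP defines the endpoint on the full index: "Proportion of participants with a state of complete remission, defined as SLEDAI-2K score (PI) =0, achieved without immunosuppressants". It also requires zero corticosteroid, held for 24 weeks or more.

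Section 15.6.6 makes this operational with three criteria:

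1. Current visit: "In complete remission at the visit".
2. Anchor visit, 24 or more study weeks earlier by visit label: complete remission or, where that cannot be assessed, "then in clinical remission the visit prior".
3. Visits in between: "In complete remission for all assessed visits between (1) and (2). – Note assessment can be missing".

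Section 15.6.5 has the parallel rule for sustained clinical remission, with the fallback "if clinical remission cannot be assessed at that visit, then in clinical remission at the visit prior". Section 15.6.4 treats disease control the same way: the substitute visit must be in disease control.

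The first addendum touches 15.6.6 only for missing SLEDAI-2K item scores. The second addendum keeps the output as Table 22.23 (old number 22.19) and lists no modification.

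**The concern.** Complete and clinical remission are different states. Complete remission needs zero on every SLEDAI-2K item. Clinical remission drops the two serological items. The fallback in criterion 2 therefore relaxes the definition at one end of the 24-week period, and only for participants whose anchor visit is not assessable. The wording looks carried over from 15.6.5.

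A programmer who follows the text would produce a table that does not measure what its title states. Formal comparisons on this endpoint are planned at Week 104 and for any time in Year 2, so both would inherit the relaxed definition. Protocol section 10.2 describes remission and disease control as rare. Where responders are few, a small number of misclassified participants could shift the proportions visibly.

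**Working it through.** The plan gives no figure to reproduce. The check compares the definitions and then applies the rule to the visit schedule.

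**How far the two states differ.** Section 15.6.3 scores 24 items for the full index: "The maximum theoretical score is 105". For the clinical version, with 22 items: "however the maximum theoretical score is now 101". The difference is 105 − 101 = 4 points, all serological. The other requirements (no treatment failure, no withdrawal, zero corticosteroid) are the same for both states, so serology is the only thing relaxed.

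**Comparison of the three rules.**

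| Section | State at current visit | State at substitute visit |
|---|---|---|
| 15.6.4 | disease control | disease control |
| 15.6.5 | clinical remission | clinical remission |
| 15.6.6 | complete remission | clinical remission |

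Only 15.6.6 switches state.

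**Whether criterion 3 closes the gap.** It does not. It covers visits between (1) and (2), and the substitute visit is itself (2).

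**Effect at each Year 2 visit.** I used the investigator's SLEDAI-2K schedule. In each case the anchor is missing, the substitute is in clinical remission only, and every later visit is in complete remission. The documented span is the reporting week minus the first visit after the anchor.

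| Reporting week | Anchor | Substitute | Documented complete remission |
|---|---|---|---|
| 60 | 36 | 32 | 60 − 40 = 20 weeks |
| 64 | 40 | 36 | 64 − 44 = 20 weeks |
| 72 | 48 | 44 | 72 − 52 = 20 weeks |
| 80 | 52 | 48 | 80 − 60 = 20 weeks |
| 88 | 64 | 60 | 88 − 72 = 16 weeks |
| 96 | 72 | 64 | 96 − 80 = 16 weeks |
| 104 | 80 | 72 | 104 − 88 = 16 weeks |

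As written, every row is sustained. With complete remission required at the substitute visit, none is.

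**Patterns at Week 104.** Give each of Weeks 72, 80, 88, 96 and 104 one of four states: complete remission, clinical remission only, neither, or missing. That makes 4⁵ = 1024 patterns. Week 104 must be in complete remission, and Weeks 88 and 96 must each be in complete remission or missing (2 × 2 = 4 ways).

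- Week 80 in complete remission, Week 72 in any state: 4 × 4 = 16 patterns.
- Week 80 missing, rule as written, Week 72 in complete or clinical remission: 2 × 4 = 8 patterns.
- Week 80 missing, complete remission required at Week 72: 1 × 4 = 4 patterns.

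The total is 16 + 8 = 24 as written and 16 + 4 = 20 when corrected. The 4 patterns lost all have Week 72 in clinical remission only and Week 80 not assessable.

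**Whether the fallback can be triggered.** Section 2.2 of the first addendum allows only the 8 laboratory items to be carried forward, and 15.6.3 limits this to 35 days. The target days for Weeks 72 and 80 are 505 and 561, which is 56 days apart. A laboratory item missing at Week 80 therefore cannot be filled from Week 72 when visits are on target. Protocol section 9.4 also bars efficacy assessments at telephone or video contacts.

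**The case against.** The strongest reply is that this is a slip of one word. The section title, criterion 1, the first half of criterion 2, criterion 3 and the endpoint statements all say complete remission. Nothing suggests that a looser definition was chosen, and the program may already be right. That is likely, but the criterion is the operative derivation rule and no other text overrides it.

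The scope is also narrow, and this stands. Three things must coincide: the anchor is not assessable, serology is active at the one preceding visit, and the full index is zero at every later assessed visit. Current serological activity is never tolerated.

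No count of affected participants can be given, and the wider ±28-day visit windows were meant to limit missed visits. The wording is the same for all arms, so no direction of bias is shown.

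The extreme case, in which Weeks 80, 88 and 96 are all missing, arises mainly from criterion 3's tolerance of missing visits. Complete remission at Weeks 72 and 104 alone would still qualify after the correction, so that weakness should not be charged to this word.

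These arguments limit the weight of the point. They do not make the text correct.

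**Conclusion.** The concern holds. As written, 15.6.6 can classify a participant with active serology at the substitute anchor visit as in complete remission for 24 weeks or more, when only 16 to 20 weeks of it are documented. At Week 104, 4 of the 24 qualifying patterns depend on this word.

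The conclusion assumes that the rule is programmed literally and that the anchor is the nearest earlier scheduled visit 24 or more weeks back. How many participants fit those patterns is unknown.

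The point is minor. The endpoint carries no multiplicity control, and the primary and both major secondary analyses do not use the rule. Complete remission by visit (Table 22.22) is also unaffected.

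**What to change.** In criterion 2 of 15.6.6, require complete remission at the substitute visit, in line with 15.6.4 and 15.6.5. Confirm that the program for Table 22.23 does this. If it already does, a one-line clarification on file is enough.

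The cost is one word, a code check and, because the SAP is approved, a short addendum or documented programming note. No new data are needed.
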